### **Statistical Analysis Plan**

A redcap database will be created to collect all data fields and insure data integrity. Statistical support will be through a qualified statistician from the Clinical and Translational Science Institute of Southeast Wisconsin, [name]. We plan to compare continuous variables such as change in platelet count; platelet response to TRAP, U46619, and CRP; length of stay; length of mechanical ventilation; transfusion volumes; total hospital cost; and methemoglobin levels with either a Mann Whitney test or t-test. A chi-square analysis will be used for dichotomous variables such as mortality and need for ECMO. Multivariate or regression analysis will be done as needed to control for significant cofounders such as surgical complexity scoring, age, gender, race, ethnicity, weight, and presence of known genetic disorder.

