## **Protocol**

To complete the aims and objectives of this project we are planning a pilot randomized, double blinded, placebo controlled clinical trial of nitric oxide added to the sweep gas of the oxygenator during cardiac surgery requiring CPB in infants.

Inclusion Criteria: Infants less than one year of age undergoing cardiac surgery with the use of cardiopulmonary bypass.

Exclusion Criteria: Prior surgery requiring CPB within the same hospitalization, pre-operative need for ECMO or mechanical circulatory support, known hypersensitivity to nitric oxide, known hemostatic or thrombotic disorder that results in an altered transfusion/anticoagulation protocol

Equitable subject selection: All patients will be considered for eligibility that meet the inclusion/exclusion criteria regardless of race, gender, or ethnic background. Non-English speaking patients will be considered for inclusion if a suitable consent form can be approved prior to their surgical procedure. A Spanish language short form will be submitted along with the initial study as we anticipate some eligible subjects will be Spanish speaking only. Other languages encountered in eligible patients will be considered on an individual basis and if a suitable consent form can be drafted and approved prior to the patient's surgical date, they will be considered for enrolment.

Sample Size: 40 patients equally distributed amongst the treatment and placebo groups

Power Calculation: using 0.05 as type 1 error tolerance and previous data from neonatal CPB studies, a minimum sample size of 12 patients is necessary to detect a difference of a change in platelet count (Specific Aim 1) of 50 with a power of 91%.

Sample size justification: In order to maximize the ability to estimate a sample size for a larger multi-institutional trial (Specific Aim 2) we need to maximize the number of patients enrolled within this local pilot trial. Approximately 120 infants annually meet the inclusion/exclusion requirements annually at CHW. Given experience with prior interventional studies in this population, we anticipate a consent rate of approximately 33%. Therefore we anticipate being able to enroll 40 patients into this trial within one year.

Randomization: Stratified to insure the number of patients with Society of Thoracic Surgery (STS) Mortality Class 1-3 and 4-5 surgeries are equally distributed.

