Justification for stratification of randomization: The complexity of congenital cardiac surgery is known to significantly impact morbidity and mortality (16). In order to insure an equal distribution of patients with this known confounder among groups we will stratify the randomization to insure an equal distribution to active and placebo groups.

Recruitment: The PI and co-investigators have access to the cardiac surgical scheduling coordinators. We will be in contact with them and browse the list of scheduled surgical patients at the weekly surgical conference. The PI and co-investigators are also active clinicians within the cardiac intensive care unit and will be looking for eligible patients amongst the census of the intensive care unit within the normal course of their clinical duties. No fliers or published materials will be used. If the patient has an identified primary cardiologist at the time they are deemed to be eligible, we will contact them prior to approaching the patient/family to answer any questions they would have.

Treatment: A minimum sweep gas flow of 2.5 L/min will be used in all patients with CO2 added to maintain PaCO2 35-40 mmHg. All patients will have an INOmax DSIR device in line with the sweep gas. Nitric oxide at a dose of 20 ppm will be added to the sweep gas of the treatment group from the initiation to the conclusion of CPB. The placebo group will not receive nitric oxide but will be connected to the INOmax DSIR device.

The INOmax DSIR device and nitric oxide will be supplied by Mallinckrodt Pharmaceuticals. A letter indicating this support from Mallinckrodt is included in the package.

Blinding: All care providers involved in the clinical care of the patient will be blinded to treatment group (and methemoglobin levels) for 30 days post-operatively or hospital discharge (whichever is later). A single study staff (perfusionist or respiratory care practitioner) will be responsible for nitric oxide delivery according to the randomization scheme outlined above.

Study Measurements (Primary objectives in **bold**):

Aim 1:

Baseline and at conclusion of cardiac repair/prior to transfusion: **Change in platelet count**, platelet response to TRAP, U46619, and CRP (to be done at the Blood Research Institute)

Aim 2:

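### Change in platelet count, the Aim 1 primary measure, gets an unadjusted two-sample test; a pre-specified model with baseline count and STS stratum would usually be more precise at almost no cost.

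*Combined protocol and SAP*

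**What the plan says.** In the Protocol's Study Measurements, the change in platelet count is the bolded Aim 1 measure. It is taken together with the responses to TRAP, U46619 and CRP, at these times: "Baseline and at conclusion of cardiac repair/prior to transfusion". Every analysed infant therefore has a baseline value.

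The Randomization paragraph reads: "Stratified to insure the number of patients with Society of Thoracic Surgery (STS) Mortality Class 1-3 and 4-5 surgeries are equally distributed". The stratum is therefore also known for every infant.

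The Statistical Analysis Plan sets the comparison in one sentence. It begins "We plan to compare continuous variables such as change in platelet count; platelet response to TRAP, U46619, and CRP; length of stay" and ends "with either a Mann Whitney test or t-test". It names no covariate. A later sentence adds: "Multivariate or regression analysis will be done as needed to control for significant cofounders such as surgical complexity scoring". The list continues with age, gender, race, ethnicity, weight and genetic disorder. Baseline platelet count is not on it, and no trigger, model form or outcome is given for the regression.

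The Power Calculation says "a minimum sample size of 12 patients is necessary to detect a difference of a change in platelet count" of 50 at 91% power with a type I error of 0.05. It gives no SD.

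**The concern.** A change score fixes the slope of the end value on baseline at 1. If the true slope is lower, as is common for a repeated laboratory measure, the change score carries extra baseline noise into the treatment contrast. A chance difference D in mean baseline count then shifts the contrast by (slope − 1) × D, because subtracting baseline removes only the rest. A linear model estimates the slope instead of fixing it.

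The stratum is a smaller matter. The design balances the arms on it, but the named test ignores it. If it is prognostic for platelet count, the unadjusted test tends to be conservative.

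What is at stake is the width of the interval for the platelet effect with 20 infants per arm. Type I error and bias are not in question: averaged over randomisations, the planned contrast is unbiased. The same gap affects the TRAP, U46619 and CRP responses. They are also measured at both times, but the SAP does not say whether or how their baselines are used.

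**Working it through.** **Inputs from the documents:** 40 infants, 20 per arm; difference 50 (unit not stated); alpha 0.05 (taken as two-sided, since the plan does not say); 91% power with 12 patients (total or per arm not stated).

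**Inputs assumed:** the correlation rho between baseline and end count, and k = end SD / baseline SD. The documents give neither.

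**1. The plan's own figure.** With no SD stated, 12 patients at 91% cannot be reproduced directly, but it can be inverted. Solving the two-sample t-test power for the SD of change gives:
- 12 in total (6 per arm): SD 23.6
- 12 per arm: SD 35.4

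With these SDs, power at 20 per arm for a difference of 50 is above 99.9% and 99.1% respectively. A one-sided reading gives SDs of 27.0 and 39.7, with power at 20 per arm still 98.8% for the larger.

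**2. Variance of the two estimators.** With baseline SD sb:
- change score: sb² × (1 + k² − 2·rho·k)
- baseline-adjusted: sb² × k² × (1 − rho²)

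At k = 1 the ratio of the second to the first is (1 + rho)/2:

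| rho | 0.3 | 0.5 | 0.7 | 0.8 | 0.9 |
|---|---|---|---|---|---|
| variance ratio | 0.65 | 0.75 | 0.85 | 0.90 | 0.95 |

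Away from k = 1:
- k = 0.8, rho 0.6: 0.4096 / 0.68 = 0.602
- k = 1.2, rho 0.8: 0.5184 / 0.52 = 0.997 (slope 0.96, so almost nothing to gain)

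**3. Half-width of the 95% interval at 20 per arm.**
- Change score, 38 df: 2.024 × SD × √(2/20) = 22.7 (SD 35.4) or 15.1 (SD 23.6).
- Adjusted, 36 df, allowing for chance imbalance in baseline: 2.028 × SD × √ratio × √(2/20) × √(1 + 1/35).
 - SD 35.4: 18.6 at rho 0.3, 21.8 at rho 0.8
 - SD 23.6: 12.4 at rho 0.3, 14.6 at rho 0.8
- At k = 1.2, rho 0.8, SD 35.4: 23.0, against 22.7 unadjusted.

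**4. Check by simulation**, 20 per arm, baseline and stratum in the model, stratum given no effect. The empirical variance ratio at k = 1 ran from about 0.67 (rho 0.3) to 0.93 (rho 0.8). At k = 1.2, rho 0.8 it was 1.02-1.03. At k = 1, the mean interval width relative to the change score, and the share of trials in which the adjusted interval was narrower, were:

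| rho | width ratio | share narrower |
|---|---|---|
| 0.3 | 0.82 | 99% |
| 0.5 | 0.88 | 95% |
| 0.7 | 0.94 | 82-83% |
| 0.9 | 0.99 | 52% |

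**5. What a chance imbalance does.** At k = 1, sb = SD/√(2(1 − rho)). A baseline difference of one standard error moves the change contrast by (1 − rho) × sb × √(2/20):
- SD 35.4: 6.6 at rho 0.3, falling to 3.5 at rho 0.8
- SD 23.6: 4.4 falling to 2.4

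Against the target of 50 this is 2.4/50 = 5% to 6.6/50 = 13%.

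**The case against.** The strongest reply is that nothing is wrong. Change in platelet count is the declared measure and the one powered, the test is valid, and on the plan's implied SDs the power for 50 is already above 99%. That stands, and it is why this is an improvement and not a correction. The power figure does, however, rest on an SD that the plan never states.

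Second, the gain depends on unseen values. That also stands. With equal SDs it fades to about 1% in width at rho 0.9, and at k = 1.2 with rho 0.8 the adjusted interval is 1-2% wider. Charging both covariates for imbalance (1 + 2/35) moves the range at SD 35.4 to 18.8-22.1. The smaller charge is defensible because stratified randomisation largely balances the stratum. The downside examined is trivial and the upside is not.

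Third, the shift in step 5 is not a second harm. Correct: random imbalance is already in the standard error of the change score, so step 5 shows the same gain in another form.

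Fourth, the conditional regression sentence may cover surgical complexity, and its list is open-ended. It still fixes no model in advance and does not name baseline count, the covariate that matters most. It is also true that no gain from the stratum has been shown: the Protocol supports complexity as prognostic for morbidity and mortality, not for platelet count. The case for including the stratum is that the randomisation uses it.

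Fifth, no size can be given for the TRAP, U46619 and CRP responses, because the documents say nothing of their scale or spread. That stands.

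**Conclusion.** The concern holds. No baseline-adjusted primary analysis is pre-specified, although the data for it are collected by design. The gain is modest and depends on assumptions: with equal SDs, roughly 18% narrower intervals at rho 0.3, 6% at 0.7, and close to nothing at 0.9. It is larger if counts are less variable at the end of repair than at baseline, and absent if they are more variable and highly correlated with baseline. The absolute half-widths also rest on the SD of change inferred from the plan's 12 patients at 91% power. The benefit is precision in a pilot whose estimates are meant to inform a larger trial, not power for a difference of 50. This is a worthwhile change to a valid plan.

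**What to change.** In the Statistical Analysis Plan, name one primary analysis for Aim 1: a linear model of end-of-repair platelet count on treatment arm, with baseline platelet count and STS stratum (1-3 versus 4-5) as covariates, reporting the adjusted difference with its 95% confidence interval. Analyse the TRAP, U46619 and CRP responses in the same form, each with its own baseline. Keep the Mann-Whitney test on the change as a named sensitivity analysis. This also settles, for the primary measure, the open choice between two tests.

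The cost is SAP wording and two residual degrees of freedom (38 to 36). No new measurement, visit or patient is needed.

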**30 day (all cause) mortality, length of hospital stay post-operatively**, transfusion volumes of platelets and pRBCs, total number of transfused products, length of mechanical ventilation post-operatively, vasoactive infusion score (highest within the first 24 hours post-operatively), need for ECMO within 48 hours post-operatively, and total hospital cost.

Aim 3:

Baseline, at conclusion of CPB, and upon arrival to ICU: **Methemoglobin levels**

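### Does listing only between-arm tests for the Aim 2 outcomes leave the pilot unable to size the larger trial?

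*Combined protocol and SAP*

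**What the plan says.** Under Sample Size the protocol sets "40 patients equally distributed amongst the treatment and placebo groups". Two neighbouring paragraphs explain the number. The Power Calculation says "a minimum sample size of 12 patients is necessary to detect a difference of a change in platelet count (Specific Aim 1") and concerns Aim 1 only. The Sample size justification then gives the reason for going further: "In order to maximize the ability to estimate a sample size for a larger multi-institutional trial (Specific Aim 2"). It takes the figure of 40 from expected one-year accrual: "Approximately 120 infants annually meet the inclusion/exclusion requirements annually at CHW", of whom about a third are expected to consent.

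Under Study Measurements, bold type marks the primary objectives. For Aim 2 the bold items are "30 day (all cause) mortality, length of hospital stay post-operatively".

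The Statistical Analysis Plan is one paragraph. For the binary outcomes it says: "A chi-square analysis will be used for dichotomous variables such as mortality and need for ECMO". The continuous outcomes are compared: "length of stay; length of mechanical ventilation; transfusion volumes; total hospital cost; and methemoglobin levels with either a Mann Whitney test or t-test". Adjustment is optional: "Multivariate or regression analysis will be done as needed to control for significant cofounders". The paragraph mentions no estimate to carry forward, no interval and no sizing calculation. The full wording of Specific Aim 2 is not in the text available for this review, so it could not be checked whether a sizing outcome is named there.

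**The concern.** A pilot that exists partly to plan a larger trial should deliver planning quantities: a control event rate, an SD, and a measure of how well each is known. Here the stated reason for enrolling well beyond the Aim 1 minimum is planning, yet the analysis section speaks only of comparing arms. Read literally, it would give p-values from 20 against 20. For mortality these would say almost nothing.

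The choice of sizing outcome is also open, and it matters. Mortality and length of stay imply later trials of very different size, and 40 infants inform the two very unequally. If the choice were made after seeing which arm did better, the larger trial could be built on a chance difference.

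**Working it through.** **The plan's own figure.** 120 eligible × 0.33 consenting = 39.6, or 120/3 = 40. So 40 is what one year should yield, not the result of a power or precision target for Aim 2. The surplus over the Aim 1 minimum is 40 − 12 = 28 infants, or 40 − 24 = 16 if 12 means per arm.

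The documents give no event rates or SDs. All rates and effect sizes below are assumptions.

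**1. What the tests can show at 20 v 20** (two-sided 0.05)

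Mortality, by exact enumeration of all 21 × 21 tables:

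| Assumed rates | Pearson | Fisher |
|---|---|---|
| 10% v 5% | 5.4% | 1.7% |
| 15% v 5% | 15.4% | 7.0% |

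Length of stay, t-test with 38 df and noncentrality d√(20/2):

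| Difference | Power |
|---|---|
| 0.5 SD | 34% |
| 0.8 SD | 69% |
| 0.91 SD | 80% |

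The mortality test is nearly powerless. The length-of-stay test is weak but not empty.

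**2. What 40 infants can contribute to planning**

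*Mortality.* With 2 deaths in 40, the exact (Clopper-Pearson) 95% interval is 0.6% to 16.9%. To detect a halving with 80% power, the number per arm is

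n = [1.96√(2p̄(1−p̄)) + 0.842√(p₁(1−p₁) + p₂(1−p₂))]² / (p₁−p₂)², with p₂ = p₁/2 and p̄ = (p₁+p₂)/2.

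- p₁ = 5%: 906 per arm
- p₁ = 16.9% (upper limit): 242 per arm
- p₁ = 0.6% (lower limit, unrounded 0.611%): 7,667 per arm

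The range is 7,667/242, about 32-fold. These values treat the pooled pilot rate as the later trial's control rate, which is right only if treatment had no effect in the pilot. If treatment halves mortality, a pooled 5% means 6.7% v 3.3%, and n is about 670 (range 172 to 5,741). The width of the range is the message, not any single n. At a true rate of 5% in both arms, the chance of no deaths at all is 0.95⁴⁰ = 13%.

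*Length of stay.* With 38 df, the 95% limits for the SD are √(38/56.90) = 0.82 and √(38/22.88) = 1.29 times the estimate. Since n is proportional to SD², it runs from 0.67 to 1.66 times its point value, a 2.5-fold range. For example, a difference of 0.5 SD needs 63 per arm, with a range of 0.67 × 63 = 42 to 1.66 × 63 = 105. This assumes that all 40 infants contribute and that stay is roughly normal on the scale used (log days is the likely choice).

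**3. Does the listed analysis withhold these inputs?**

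| Planning input | Where the listed analysis produces it |
|---|---|
| Mortality and ECMO rate by arm | The cells of the chi-square table |
| SD of length of stay | Computed by the t-test; a simple summary of the same column if Mann-Whitney is used |
| Interval for either | A function of those same numbers |

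No input needs data that the trial does not collect.

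**4. Is the chi-square itself a fault with few events?** At 20 v 20, the uncorrected Pearson test has true size 0.012 at a common rate of 5%, 0.039 at 10%, and at most 0.053 (near 31%). Sparse counts do not inflate type I error materially. Fisher's test would be more conservative still (0.002 and 0.012 at the first two rates).

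**The case for a change.** The best case for a change is that a plan should name its main deliverable. It would cost a few sentences to fix the sizing outcome, the scale for length of stay, how in-hospital deaths enter that outcome, and a rule that the next trial is sized from a clinically relevant difference. Settling these beforehand removes any suspicion that the choice followed the results. It would also warn readers that a mortality rate from 40 infants cannot size a trial alone.

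Much of this stands as good practice. The plan is thin, the stated purpose and the listed analyses are not joined up, and the mortality p-value will be uninformative. Three things limit its force.

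- The omission does not remove the inputs. Anyone sizing the next trial must start from the rates and SDs, and no sentence in the plan directs them to the observed difference instead.
- The candidates are already down to two by the bold type. Choosing between them on pilot variability, without using the arm difference, is a legitimate use of a pilot.
- It is too strong to say that the 28 (or 16) infants above the Aim 1 minimum serve Aim 2 only. All 40 also supply platelet data for Aim 1 and methemoglobin data for Aim 3.

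**Conclusion.** No change follows. The plan leaves out detail that a competent analyst supplies as a matter of course. The rates and SDs come with the listed comparisons, and no stated rule produces a wrong result. The real limitation is the precision of 40 infants: about 32-fold uncertainty in a mortality-based sample size, against 2.5-fold for one based on length of stay. Rewording the analysis section would not alter either figure.

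The 32-fold figure assumes 2 deaths in 40, a halving as the target, and the pooled rate used as the control rate. The 2.5-fold figure assumes 38 df and a scale on which stay is roughly normal. The conclusion that no change is needed rests on neither. It rests on the data being collected and on the plan nowhere committing to size the next trial from the observed effect. A commitment of that kind in the full statement of Specific Aim 2 would reopen the point.

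### Randomisation is stratified by STS class, but the planned tests of continuous outcomes ignore the stratum; where class predicts the outcome, precision and power are lost

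*Combined protocol and SAP*

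**What the plan says.** The Randomization paragraph of the Protocol reads: "Stratified to insure the number of patients with Society of Thoracic Surgery (STS) Mortality Class 1-3 and 4-5 surgeries are equally distributed". The justification that follows gives the reason: "The complexity of congenital cardiac surgery is known to significantly impact morbidity and mortality". It calls complexity a confounder to be balanced between arms: "In order to insure an equal distribution of patients with this known confounder among groups".

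The Statistical Analysis Plan compares the continuous outcomes (change in platelet count, platelet responses, length of stay, ventilation time, transfusion volumes, cost, methemoglobin) "with either a Mann Whitney test or t-test". Neither test uses the stratum. Surgical complexity is listed first among possible covariates, under this sentence: "Multivariate or regression analysis will be done as needed to control for significant cofounders". There is no rule for when regression is needed, no statement that the covariate is the randomisation stratum, and no statement of whether the adjusted or the unadjusted result is primary.

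**The concern.** Stratified allocation makes the arms alike in class mix, so differences between classes largely cancel out of the treatment difference. A t-test or Mann-Whitney test that ignores class does not know this, and its standard error still contains the between-class spread. Where class predicts the outcome, the test is conservative, the interval is too wide, and power paid for by the design is not collected.

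The protocol asserts prognostic value for morbidity and mortality, without a strength, and does not assert it for platelet change. The loss is therefore most plausible for length of stay, one of the bold measures of Aim 2 ("length of hospital stay post-operatively"), and for that aim's other continuous clinical outcomes. The pilot is also meant to inform the size of a larger trial, and an SD that ignores class overstates the number needed by a trial that adjusts for it.

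**Working it through.** **Inputs from the documents.** 40 patients, 20 per arm; two strata; type I error 0.05 (two-sided assumed); a platelet difference of 50 with 12 patients and 91% power.

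**Assumptions, not in the documents.** Class explains a share R² = 0.1, 0.2 or 0.3 of outcome variance; 20%, 30% or 50% of patients are in class 4-5; true effects are 0.6 and 0.9 SD. Effects are in units of the total within-arm SD, set to 1 and held fixed as R² changes. Allocation is balanced within class.

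**Step 1: the plan's own figure.** The Power Calculation says "a minimum sample size of 12 patients is necessary to detect a difference of a change in platelet count" of 50. No SD is given, so the figure cannot be reproduced, only back-solved from the noncentral t:
- 12 per arm: effect 1.41 SD, so SD = 50/1.41 = about 35.4.
- 12 in total: effect 2.12 SD, so SD = 50/2.12 = about 23.6.

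**Step 2: true and estimated variance.** With balance within class, the variance of the treatment difference is (1 − R²)(1/20 + 1/20) = 0.1(1 − R²). The unstratified pooled variance has expectation (1 − R²) + 40R²/38. Its ratio to the within-class variance is:
- R² = 0.1: (0.9 + 0.105)/0.9 = 1.12
- R² = 0.2: (0.8 + 0.211)/0.8 = 1.26
- R² = 0.3: (0.7 + 0.316)/0.7 = 1.45

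The square roots are about 1.06, 1.12 and 1.20, so t-intervals are 6%, 12% and 20% wider than adjusted ones.

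**Step 3: size.** To reject, the difference must exceed 2.024 × √ratio, that is about 2.14, 2.28 and 2.44 true standard errors. The two-sided tail areas on 38 df are about 3.9%, 2.9% and 2.0%. Simulation (40,000 trials per setting, across the three class shares) agrees, as the table shows.

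**Step 4: power.** Adjusted power comes from the noncentral t on 37 df with noncentrality d/√(0.1(1 − R²)). For d = 0.9 this is 3.00, 3.18 and 3.40. For d = 0.6 it is 2.00, 2.12 and 2.27. The other rows come from the simulations; the detectable differences come from numerical power calculation.

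| | R² = 0.1 | R² = 0.2 | R² = 0.3 |
|---|---|---|---|
| Size, t-test | 3.8-4.0% | 2.8-3.0% | 1.8-2.1% |
| Coverage of nominal 95% t-interval | 96% | 97% | 98% |
| Power at 0.9 SD: t-test / with stratum | 80 / 83% | 81 / 87% | 83 / 91% |
| Power at 0.9 SD: Mann-Whitney / van Elteren | 77-78 / 80% | 78-79 / 84-85% | 80-81 / 89% |
| Power at 0.6 SD: t-test / with stratum | 45 / 49-50% | 45 / 54% | 44 / 60% |
| Power at 0.6 SD: Mann-Whitney / van Elteren | 42-43 / 46-47% | 42-43 / 51% | 41-42 / 56-57% |
| Difference detectable with 80% power: t-test / with stratum | 0.90 / 0.86 SD | 0.89 / 0.81 SD | 0.87 / 0.76 SD |

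Size with the stratum in the model is 4.7-5.2% throughout. The rank-test rows also hold for a lognormal outcome if R² and the effect are taken on the log scale.

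**Step 5: weak prediction.** At R² = 0.05, t-test size is about 4.5%, and power at 0.91 SD is 80.7% against 82.1% adjusted. At R² = 0 the t-test and the adjusted model agree to about 0.1 point.

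**Step 6: how balance is achieved.** With permuted blocks of 4 left incomplete and a random class share averaging 30%, t-test size is 4.1%, 2.9% and 2.3%, and power at 0.9 SD is 80%, 81% and 83% against 83%, 87% and 91%. With simple randomisation within strata, t-test size returns to about 5% (5.3%, 5.3%, 4.9%), but power is still lost: 78% against 81%, 85% and 90%.

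**Step 7: platelet change.** At 1.41 SD with 20 per arm, power is 99.4%, 99.6% and 99.7% unadjusted against 99.6%, 99.8% and 99.9% adjusted. At 2.12 SD both are 100%.

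**Step 8: planning the larger trial.** The overall variance exceeds the within-class variance by the ratios in Step 2. A variance estimated on 38 df has a 95% interval of 0.67 to 1.66 times the estimate (38 divided by the chi-square quantiles), so sampling error exceeds this excess.

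**The case against.** The strongest reply is that little of importance is affected. The only outcome with a power calculation, platelet change, loses at most about 0.2 point. The documents do not say that class predicts platelet change, and give no reason to expect it for platelet responses or methemoglobin. Mortality and ECMO lie outside these calculations. That leaves length of stay as the one bold outcome, plus secondary Aim 2 measures, in a pilot whose 40 patients were not chosen to power those tests. Every loss depends on an assumed R², and at 0.05 or below it is small. The 16-point loss needs R² = 0.3 and a 0.6 SD effect together, and even the adjusted power is then only 60%. Conservatism requires real balance within class, and no blocking method is stated. The SAP specifies tests, not intervals, and it already names complexity as a covariate.

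Most of this stands as a limit on size. The range does start near zero, and within-class balance is a condition for conservatism. Balance is, however, the stated aim of the stratification, and power is lost even under simple randomisation within strata. Listing complexity as a possible covariate does not settle the matter, because without a rule or a named primary analysis the choice is made after the data are seen. The interval point applies to whatever intervals accompany the tests.

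**Conclusion.** The concern holds, as an efficiency point that should be acted on rather than a threat to validity. Omitting the stratum does not inflate type I error. For continuous outcomes that class predicts with R² of 0.1 to 0.3, the t-test loses about 3, 6 and 8 points of power at 0.9 SD, and about 4, 10 and 16 points at 0.6 SD. The loss shrinks towards zero as R² does. These sizes rest on the assumed R², effects and class shares; the direction does not depend on their exact values.

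The figures concern continuous outcomes only and should not be carried over to 30-day mortality or ECMO, where events may be few. For sizing the larger trial this is a reporting point, since the excess in variance is smaller than the uncertainty of a pilot estimate.

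**What to change.** For each continuous outcome, name as primary a linear model with treatment and the STS randomisation stratum (1-3 versus 4-5). For outcomes expected to be skewed, such as length of stay, name a stratified rank test such as van Elteren instead. Fix the choice per outcome before unblinding, and label models with other covariates as sensitivity analyses. For Aim 2, report the within-stratum SD beside the overall SD.

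This needs SAP wording only. It uses one degree of freedom in the linear model and no new data, because class is already recorded for randomisation. If class proves unrelated to the outcome, the linear model gives up about 0.1 point of power (0.1 to 0.3 with incomplete blocks) and the stratified rank test about 1 point.

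### Open-ended covariate adjustment and a chi-square test do not suit the few deaths and ECMO events expected in 40 infants; fix a short covariate set in advance and report binary outcomes exactly

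*Combined protocol and SAP*

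**What the plan says.** The Statistical Analysis Plan assigns a t-test or Mann Whitney test to continuous outcomes. For binary outcomes it says: "A chi-square analysis will be used for dichotomous variables such as mortality and need for ECMO". The next sentence is the adjustment rule: "Multivariate or regression analysis will be done as needed to control for significant cofounders such as surgical complexity scoring, age, gender, race, ethnicity, weight", with known genetic disorder as the seventh factor.

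The rule names no outcome and excludes none. It does not say when adjustment is needed, what makes a factor significant, how race or surgical complexity is coded, or what happens when events are few. The list is illustrative, so more than seven factors could be used.

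The Protocol section sets the size: "Sample Size: 40 patients equally distributed amongst the treatment and placebo groups". Randomization is stratified by STS mortality class (1-3 versus 4-5). Under Study Measurements, 30-day mortality is in bold, which marks it as a primary objective (Aim 2). Need for ECMO within 48 hours is listed there without bold. No expected rate is given for either.

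**The concern.** Twenty infants per arm will yield few deaths or ECMO runs. A logistic model with treatment and seven or eight covariate terms would then often be separated: some combination of terms predicts the events perfectly, and maximum likelihood has no finite solution. The chi-square test is also weak ground when expected counts are this small.

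For continuous outcomes, each covariate that explains nothing costs precision. A set picked by significance after the data are in also leaves the adjusted result open to choice.

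The sample size justification says that Aim 2 is to inform a larger multi-institutional trial. An infinite or unstable adjusted odds ratio for mortality could not serve that purpose.

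**Working it through.** **Inputs from the documents.** N = 40, 20 per arm. This agrees with the recruitment figures: 120 eligible per year × 0.33 consent = 39.6. The 91% power figure for platelet count has no stated SD and does not bear on this point.

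**Assumed, because the documents are silent.** Event rates of 5% to 15%, which give 2 to 6 expected events (40 × 0.05 to 40 × 0.15). For the simulation: 35% in STS class 4-5, age-weight correlation 0.93, race in three levels, and assumed frequencies for the other factors.

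**Step 1. Sparse events alone.** With treatment as the only term, the odds ratio is non-finite if either arm has no event. (The chance that all 20 in an arm have one is negligible.) With rate p in both arms the probability is 1 − [1 − (1 − p)^20]²:
- 5%: 0.95^20 = 0.358; 1 − 0.642² = 59%
- 10%: 0.90^20 = 0.122; 1 − 0.878² = 23%
- 15%: 0.85^20 = 0.039; 1 − 0.961² = 8%

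Simulation gave 59%, 26% and 7%, which agrees within sampling error.

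**Step 2. Full list.** Simulated 40-infant trials were tested for separation by linear programming, with treatment plus eight covariate columns. The range in brackets covers the other simulation runs, which used different covariate frequencies, an age-weight correlation of 0.8 or 0.93, race in two or three levels, and covariates related or unrelated to outcome.

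| Event rate | Any coefficient non-finite | Treatment odds ratio non-finite | Treatment-only model (exact) |
|---|---|---|---|
| 5% | 99% (97 to over 99) | 78% (78 to 84) | 59% |
| 10% | 94% (85 to 95) | 41% (41 to 52) | 23% |
| 15% | 85% (66 to 88) | 15% (15 to 30) | 8% |

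At 20%, all coefficients were finite in 26% to 52% of trials. Monte Carlo error is up to about 2.5 percentage points with 400 trials per setting.

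**Step 3. Chi-square.** With D events in total, the expected count per arm is D/2, which is below 5 unless D is at least 10. For a binomial with n = 40, P(D ≤ 9) is above 99% at rates of 5% and 10%, and about 93% at 15%.

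**Step 4. Continuous outcomes.** With k covariates unrelated to treatment, the variance of the treatment effect is multiplied on average by 37/(37 − k), and by (1 − R²) for the variance they explain. The interval width relative to the unadjusted one is √[(1 − R²) × 37/(37 − k)] × t(38 − k)/t(38).
- k = 7: 37/30 = 1.23 and t ratio 2.040/2.024, so the ratio is 1.12 at R² = 0, 1.00 at 0.2, 0.94 at 0.3 and 0.79 at 0.5. Break-even R² is about 20%.
- k = 8 (race on 2 df): 37/29 = 1.28; ratio 1.14 at R² = 0; break-even about 23%.
- k = 2 (stratum and baseline): 37/35 = 1.06 and t ratio 2.028/2.024; ratio 1.03 at R² = 0; break-even about 6%.

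Simulation gave variance factors of 1.23 for seven covariates and 1.28 for eight, in line with the formula.

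**The case against.** A reader might infer that the plan applies all seven factors to every outcome, so that an adjusted mortality or ECMO odds ratio is almost never finite. The text does not support that. The rule is conditional and illustrative: a model with one covariate complies with it, and so does no model at all. The stated test for mortality and ECMO is the unadjusted chi-square. Almost never is also too strong for the treatment odds ratio. A sparse race or genetic-disorder cell can diverge while the treatment term stays finite, and at a 10% rate that term is finite in about half of trials or more. With no event rate in the documents, no single figure can be claimed.

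It is fair to add that the covariates are not the main culprit. At 5%, 59 of the 78 percentage points are there with no covariates at all. Penalized or exact regression would also handle separation.

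A reader might further infer that adjusting continuous outcomes loses precision. That holds only if the covariates explain little. The Protocol's justification for stratification describes surgical complexity as a known influence on morbidity and mortality, so some explained variance is likely. Correlation between age and weight mainly inflates their own standard errors, not that of the treatment effect.

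All of this stands, and it narrows the point. It does not remove it: the rule still permits the large model for a bolded outcome, sets no criterion for selection, and pairs a handful of events with chi-square.

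**Conclusion.** The point holds as a matter of what the plan leaves open. Over event rates of 5% to 15%, a full-list logistic model would usually have some non-finite coefficient (about 99% falling to 85% of trials). Its treatment odds ratio would be non-finite in about 78%, 41% and 15% at 5%, 10% and 15%, and in up to 84%, 52% and 30% under other covariate assumptions. Shrinking the model alone would not cure this, and chi-square is poorly suited over the same range.

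For continuous outcomes the worst loss is modest: intervals about 12% wider with 7 df, or 14% with 8 df. It turns into a gain once the covariates explain more than 20% to 23% of the variance. The stronger case for a fixed set there is that selection should not depend on the data.

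Event rates and covariate frequencies are assumptions; N and the list of factors come from the documents. Adjustment is optional and the main comparisons are unadjusted, so this is a change that should be made, not a flaw that invalidates the design.

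**What to change.** Amend the Statistical Analysis Plan as follows.

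1. **Mortality and ECMO:** report counts by arm and the rate difference with an exact confidence interval, in place of chi-square. State that no maximum-likelihood multi-covariate model will be fitted. Label any adjusted analysis exploratory and use a penalized or exact method.
2. **Continuous outcomes:** replace data-driven choice of confounders with a short set fixed in advance: the STS stratum used in randomization, plus the outcome's baseline value where one is measured (platelet count, platelet responses, methemoglobin). Name the outcomes to be adjusted.
3. **Further covariates:** age, weight or another factor may be added at the sponsor's choice, with its coding, if fixed before unblinding. The remaining factors describe the arms.

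The cost is wording only, with no change to sample size or data collection. The two-covariate set widens intervals by about 3% at worst. The downside is that a chance imbalance in a dropped factor is described and not modelled.
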